3.3 Exclusion criteria

3.3.1 Exclusion criteria

A potential subject who meets any of the following criteria will be excluded from participation in this study:

- Patients with a clear anatomical or other urological cause for OAB (e.g. bladder cancer, benign prostate hyperplasia (BPH), prostate cancer, urolithiasis, chronic or acute urinary tract infections (UTI), neurological disease).
- Patient with severe stress incontinence
- Pregnancy

3.3.2 Exclusion criteria healthy volunteers

• Current or past diagnosis of lower urinary tract symptoms;

- No more than one urinary tract infection in half a year.
- Start-up of regularly used medication from one month before inclusion until the end of study participation.

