Main study endpoints: The main study outcome comprehends the psychometric properties of the PROM for symptom assessment of OAB symptoms. Secondary outcomes are increase in ESM score for OAB symptoms and environmental and psychosocial factors (*e.g.* as measured by the PROM) from one time point (t-1) to the next (t).

Burden, risks and benefits: The burden that is associated with participation in this study comprises completing the PROM questionnaire several times a day, which interrupts daily life due to its random character. Furthermore, the burden is limited to completing a SR-BD and other symptom questionnaires. Most importantly, participating does not bring along

important health related risks. However, awareness could trigger symptoms and therefore be considered as a burden. Nevertheless, for the patients it could be beneficial too to know what triggers complaints, to cope better with their disease.

INTRODUCTION AND RATIONALE

The overactive bladder syndrome (OAB) is defined by the International Continence Society (ICS) as a symptom complex of urgency, usually with frequency and nocturia (awakening at night to void), with (OAB wet) or without (OAB dry) urinary urgency incontinence. Urgency is the complaint of a sudden compelling desire to pass urine, which is difficult to defer⁵. OAB is clinically diagnosed using the ICS criteria of \geq 8 micturitions and at least 1 urgency episode per 24 hours.

It is estimated that approximately 16-17% of the adult population of the Western world is affected by OAB ^{6,7}. The incidence of OAB, both wet and dry increases by age ⁸⁻¹⁰, and because of the worldwide ageing of the population, the number of adults affected by urinary urgency incontinence (UUI) would increase ¹¹. The health care costs of OAB are high ¹², and work productivity can be significantly impacted as well ¹³. In addition, OAB can be associated with comorbidity and increased mortality^{14,15}. Furthermore, OAB with and without incontinence has been associated with significantly lower quality of life scores compared to matched controls without voiding complaints⁸. It is of particular interest that OAB does not only affect the patients, but also has an impact on family members ¹⁰.

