Hypothesis: Since OAB symptoms might fluctuate within the study period, we do not expect to find perfect test-retest reliability (i.e. test-retest reliability coefficients close to 1.00). However, it is hypothesized that symptoms will show certain subject-specific patterns, so consistency between the first half-week and the second-half week is expected. Therefore, we hypothesize to find test-retest reliability coefficients around 0.70-0.80.

5. To assess how well the developed ePRO differentiates between OAB and healthy subjects, by determining the accuracy of the discriminatory model using a confusion matrix.

Hypothesis: We hypothesize that the accuracy of the ePRO to differentiate between OAB and healthy subjects will be comparable with ICS criteria, i.e. moderately to good. There are no studies that examined the sensitivity or specificity of these criteria. However, since OAB-like symptoms often occur in healthy subjects we expect that the ePRO might classify some healthy subjects as OAB (i.e. false positives) resulting in moderate sensitivity and high specificity.

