3.2 Inclusion criteria

3.2.1 Inclusion criteria OAB patients

Patients between 18-70 years with either subjectively experienced OAB for which they have sought medical help or have been diagnosed with OAB by a medical physician. Participants need to be able to understand written Dutch and speak the Dutch language, since the ESM app will be conducted in Dutch. They also have to understand how to practice the ESM tool.

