3.2.2 Inclusion criteria healthy volunteers

- Age between 18 and 70 years;
- Male and female
- Ability to understand and speak Dutch;
- Ability to understand how to utilize the ESM tool.

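### Volunteers are screened for a diagnosis but not for symptoms, so undiagnosed people who meet the protocol's OAB rule can be labelled healthy and bias specificity downward

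*Combined protocol and SAP*

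**What the plan says.** **Volunteers.** Section 3.3.2 has one exclusion that concerns bladder symptoms: "Current or past diagnosis of lower urinary tract symptoms". Its other two entries are "No more than one urinary tract infection in half a year" and "Start-up of regularly used medication from one month before inclusion until the end of study participation". Neither would detect urgency or frequency. Section 3.2.2 asks only for age, either sex, command of Dutch and "Ability to understand how to utilize the ESM tool". No urgency, voiding-frequency, questionnaire or diary threshold applies to volunteers.

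**Patients.** Section 3.1 has the urologist diagnose OAB with the ICS criteria, which the Summary and Introduction give as at least 8 "micturitions and at least 1 urgency episode per 24 hours". Section 3.2.1 also admits people with "subjectively experienced OAB for which they have sought medical help".

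**Use of the groups.** Section 1, Part II, objective 5 assesses discrimination with a confusion matrix. It expects that "since OAB-like symptoms often occur in healthy subjects we expect that the ePRO might classify some healthy subjects as OAB", and the same sentence calls these results false positives. Section 6 has no step that checks volunteers against the ICS rule, and no sensitivity analysis on their status.

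**Background rate.** The Introduction states: "It is estimated that approximately 16-17% of the adult population of the Western world is affected by OAB".

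**The concern.** The ICS rule is defined by symptoms and needs no earlier diagnosis. The plan applies it to patients but has no matching check for controls. A volunteer with daily urgency and ten voids who has never seen a doctor passes every listed criterion.

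If the ePRO flags that volunteer, it has done its job, yet the matrix records an error. Mislabelled controls therefore lower specificity and overall accuracy, provided the ePRO flags OAB more often than it flags people without OAB. The OAB-versus-control contrast in triggers described in section 3.1 would be diluted in the same way. With no symptom-based label for controls, a correct detection cannot be told from a real instrument error.

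**Working it through.** The plan gives no figure for mislabelled controls. Its only calculated number is the 66 patients in section 3.4: 50/(1 - 0.23) = 64.9, and with the upper cited rate 50/(1 - 0.232) = 65.1, which rounds up to 66. That figure is not in dispute.

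**Inputs from the documents**
- Prevalence p = 0.16 to 0.17 (Introduction).
- Controls n = 66 (Summary) or 35 + 35 = 70 (section 3.1).

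**Assumptions not in the documents**
- Volunteers have the general adult prevalence, and that prevalence applies to the ICS rule.
- The undiagnosed share of OAB, u, is 0.25 to 1.
- ePRO sensitivity is 0.80 and specificity 0.90. Objective 5 says only that it expects moderate sensitivity and high specificity.

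**Step 1: share of controls with OAB.** The diagnosis criterion removes the diagnosed cases, so c = p·u / (1 - p·(1 - u)). For p = 0.16 and u = 0.25, c = 0.04/0.88 = 0.0455.

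**Step 2: expected number.** n·c, for example 66 × 0.0455 = 3.0.

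**Step 3: apparent specificity.** (1 - c) × 0.90 + c × (1 - 0.80) = 0.90 - 0.70c.

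| u | c (p = 0.16 to 0.17) | of 66 | of 70 | apparent specificity |
|---|---|---|---|---|
| 0.25 | 0.045 to 0.049 | 3.0 to 3.2 | 3.2 to 3.4 | 0.87 |
| 0.50 | 0.087 to 0.093 | 5.7 to 6.1 | 6.1 to 6.5 | 0.84 |
| 0.75 | 0.125 to 0.133 | 8.2 to 8.8 | 8.8 to 9.3 | 0.81 |
| 1.00 | 0.160 to 0.170 | 10.6 to 11.2 | 11.2 to 11.9 | 0.79 to 0.78 |

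**Step 4: make-up of the counted false positives, n = 66.**
- At c = 0.0455: 66 × 0.0455 × 0.80 = 2.4 correct detections and 66 × 0.9545 × 0.10 = 6.3 real errors. So 2.4 of 8.7 (28%) are correct.
- At c = 0.17: 9.0 of 14.5 (62%) are correct.

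**Step 5: overall accuracy with 66 per group.** It falls from (0.80 + 0.90)/2 = 0.85 to (0.80 + 0.868)/2 = 0.834 at c = 0.0455, and to (0.80 + 0.781)/2 = 0.790 at c = 0.17.

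**Step 6: less severe assumptions.**
- Undiagnosed cases milder and detected with probability 0.50: specificity is 0.90 - 0.40c, which is 0.88 at c = 0.0455 and 0.83 at c = 0.17.
- Volunteer prevalence 8%, half undiagnosed: c = 0.04/0.96 = 0.042, and specificity is 0.90 - 0.70 × 0.042 = 0.87.

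**The case against.** - **The text does not show that symptomatic volunteers will enroll.** A current diagnosis could be read to include a judgement made at study entry. The documents do not say who would make it or how. This stands: such people can enter, and nothing shows how many would.
- **A reader might infer that the groups are separated only by help-seeking.** Section 3.1 does not support this, because it requires an ICS-based diagnosis for patients. The gap is on the control side.
- **The magnitudes are borrowed.** The 16-17% is a general-population figure, and the Introduction does not say which OAB definition it uses. People who answer an advertisement for healthy controls may have less OAB. On the other hand, controls are age-matched to patients and the Introduction says OAB rises with age, so the rate could also be higher. The size is therefore open; the direction is not.
- **The consequence is limited.** Section 3.1 calls the control comparison exploratory. Section 6 defines no discriminatory model or cut-off, so the calculation illustrates a classifier that is not yet specified. The 95% margin around a specificity of 0.90 with 66 controls is 1.96 × √(0.90 × 0.10/66) = 0.07, wider than the shifts of 0.03 and 0.06 at u = 0.25 and 0.50. That bears on priority, but sampling error does not remove a bias.
- **Keeping symptomatic controls is a defensible choice of spectrum.** Removing them from one group only can make specificity look too good. This stands, and is why the second matrix should not replace the first.

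**Conclusion.** The point holds in a limited form. The ICS criteria label the patients, no equivalent check applies to volunteers, and objective 5 scores every ePRO-positive volunteer as a false positive. Undiagnosed controls who meet the protocol's own rule would bias specificity and accuracy downward.

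The documents do not fix the size. The range of about 3 to 11 mislabelled controls of 66 (3 to 12 of 70), with apparent specificity of 0.87 to 0.78, depends on general-population prevalence among volunteers, an assumed undiagnosed share and an assumed ePRO accuracy. The upper end, with no OAB case diagnosed, is a ceiling. A reader might take 0.78 as a forecast, or conclude that the plan commits to reporting this as a weakness of the ePRO. Neither is supported: objective 5 states an expectation, and no reporting rule follows it.

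The Part I comparison within patients and the patients' internal consistency and test-retest results do not depend on control labels. The correction is worth making because it is cheap, not because the main results are at risk.

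**What to change.** 1. Before analysis, prespecify how the 3-day bladder diary maps to the ICS rule. The diary records a degree of urge at each void, not urgency episodes, so state which score counts as an episode and how the three days are combined.
2. Derive this flag in both groups.
3. Keep the confusion matrix on all participants. Add a sensitivity matrix that excludes controls who meet the rule, and report how many patients do not meet it.
4. Do not interpret an ePRO positive in a flagged control as an instrument error.

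The data are already planned. The Summary says bladder diaries are among the tools used to judge the ICS criteria, and the Summary, section 2 and section 4.2.3 assign the diary to participants. Section 4.2 speaks of patients, so confirm that volunteers are included.

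The cost is one definition, one derived variable and one extra table. The second matrix has slightly fewer controls. Its specificity may be optimistic, because controls are removed by a self-report from the same week and the diary is itself the Part I comparator. Both matrices should therefore be shown together.

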3. STUDY POPULATION

3.1 Population

Thirty-three male and thirty-three female OAB patients will be recruited at the outpatient Pelvic Care Centre in Maastricht UMC+ the outpatient clinic Urology at Zuyderland Heerlen/Sittard and the outpatient clinic Urology at University Hospital Antwerp. Patients will be diagnosed with OAB by their urologist using the ICS criteria for OAB⁵.

Furthermore, thirty-five male and thirty-five female healthy volunteers will be included in order to exploratively evaluate the ability of ESM to discriminate between OAB patients and healthy controls, in terms of triggers for the occurrence and/or persistence of urological symptoms. This control group will be sex- and age-matched to the group of OAB patients.

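### The urinary tract infection item in the healthy-volunteer exclusion list is worded as a qualifying condition, so read literally it excludes the wrong volunteers

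*Combined protocol and SAP*

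**What the plan says.** The relevant text is in sections 3.1 to 3.3 of the combined protocol and SAP.

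- The item stands under the heading "3.3.2 Exclusion criteria healthy volunteers" and reads "No more than one urinary tract infection in half a year".
- The same list has two other items: "Current or past diagnosis of lower urinary tract symptoms" and "Start-up of regularly used medication from one month before inclusion until the end of study participation".
- The operating rule for exclusion is printed once, under section 3.3.1: "A potential subject who meets any of the following criteria will be excluded from participation in this study". Section 3.3.2 has a heading but no lead-in sentence of its own.
- In the patient list of section 3.3.1, infection counts against entry. The examples of urological causes that exclude a patient include "chronic or acute urinary tract infections (UTI), neurological disease".
- The volunteer inclusion list in section 3.2.2 covers age, sex, language and, last, "Ability to understand how to utilize the ESM tool". It has no infection item.
- Section 3.1 gives the purpose of the volunteers: to "exploratively evaluate the ability of ESM to discriminate between OAB patients and healthy controls".

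**The concern.** An exclusion list works only if every entry describes someone who should not take part. The infection item describes someone who should. Its direction is therefore opposite to that of its heading, and whoever applies the list must either follow the words or silently correct them.

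The item matters because it helps to define who counts as healthy. Part II, objective 5 (section 1) uses the volunteers as the comparison class when the accuracy of the electronic questionnaire is judged with a confusion matrix. If the words were followed, the controls would be people with repeated infections, a group that does not fit the healthy label. If some staff followed the words and others the evident intent, the control group would not be defined consistently.

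**Working it through.** No figure in the plan depends on this item, so the check is one of logic and cross-reading.

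**1. Literal application.** Let k be the number of urinary tract infections in half a year. The item is met when k ≤ 1. Under an exclusion heading, a volunteer who meets the item is excluded. With the direction reversed and the threshold kept, the item would be met when k > 1.

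| k | As written (met if k ≤ 1) | Direction reversed (met if k > 1) |
|---|---|---|
| 0 | excluded | not excluded |
| 1 | excluded | not excluded |
| 2 | not excluded | excluded |
| 3 | not excluded | excluded |
| 4 | not excluded | excluded |

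The two columns disagree in every row. The table concerns this item alone; a volunteer must still pass the other two.

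**2. Is this a style of the list?** No. Having a diagnosis of lower urinary tract symptoms and having recently started a regular medicine are both conditions that remove a volunteer. Only the infection item states a requirement to be fulfilled.

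**3. Does the patient list point the same way?** No. In section 3.3.1 infection is a ground for exclusion. Read literally, section 3.3.2 makes the near-absence of infection a ground for exclusion.

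**4. Is it corrected elsewhere?** Sections 3.1 (population), 3.2.2 (volunteer inclusion) and 7.2.2 (volunteer recruitment) contain no infection rule. The sentence is complete and sits under its own heading, so neither redaction nor text extraction explains it.

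**5. Does any design number move?** No. Section 3.4 needs 50 usable patients and allows for 23% non-valid data. N = 50/(1 − 0.23) = 64.9, which rounds up to 65. With the upper literature figure of 23.2% that the section also cites, N = 50/(1 − 0.232) = 65.1, which rounds up to 66, the stated number. The infection item enters neither calculation.

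**The case against.** The strongest reply is that nobody would be misled. The group is called healthy throughout, and infection is a reason to exclude patients, so the intent is plain. Section 3.1 also calls the patient–control comparison exploratory, and the sample size reasoning in section 3.4 concerns patients. All of this stands and limits the weight of the point. It does not make the written rule right: objective 5 is a listed validation objective, and this is an operative eligibility criterion for its controls.

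A reader might infer more from the inversion than the documents support:

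- **That recruitment of controls would fail.** This needs staff to turn away infection-free volunteers. Nothing in the documents suggests that they would. The documents also give no infection frequency, so the share of volunteers affected cannot be calculated.
- **That specificity would be biased by infection-related urgency.** Even on the literal reading this is possible but not automatic. The item counts infections over half a year and does not require an active infection during the 7 days of experience sampling (ESM). The first item of the same list would also remove at least some symptomatic volunteers.
- **That every control enrolled under the intended reading is a protocol deviation.** The rule that meeting any criterion excludes is printed only under section 3.3.1. The heading of 3.3.2 supports the literal reading, but a monitor who reads the item by its evident intent need not record a deviation for each control. Section 8.2 says only that conduct will be monitored and a monitoring plan drafted.
- **That the electronic form repeats the error.** Section 8.1 says that inclusion and exclusion criteria are collected in Castor EDC, but the wording of the form is not in the documents.

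**Conclusion.** The point holds as an internal inconsistency in the wording of an eligibility rule. It is not a dispute about a design choice: the sponsor's threshold of one infection is not in question, only the direction in which it is applied. As written, the item excludes volunteers with 0 or 1 infection and does not exclude those with 2 or more. That contradicts the healthy control group, the other items in the list and the handling of infection in patients.

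The practical effect is probably small, on the assumption that staff apply the evident intent. No effect on the accuracy estimates or on recruitment can be put in numbers from the documents, and none is claimed here. The correction is still worth making, because the rule defines the controls for objective 5 and nothing else in the plan puts it right.

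**What to change.** Make one of two changes, keeping the sponsor's threshold:

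1. Move the sentence unchanged from section 3.3.2 to the volunteer inclusion list in section 3.2.2; or
2. Leave it in section 3.3.2 and delete its first word, so that it begins *More than one* and becomes a true exclusion.

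Then check that the matching eligibility field in Castor EDC has the same direction, and correct it only if it does not.

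The half-year period has no stated reference point, such as the date of inclusion. The sponsor could settle that in the same edit, but it is a separate and minor matter.

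The cost is one line in the protocol, notified to the ethics committee as an amendment under section 8.3 if made after approval, and one check of the form. It needs no additional participants, procedures or analyses.

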3.4 Sample size calculation

The outcome of the ESM is multidimensional; it gives information about the (urological) complaints but also the context in which the complaints arise. An inter-individual analysis can be made with the use of ESM, and because of this extensive data can be collected per patient.

An appropriate sample size can therefore not be made.

In previous literature the sample size differs from N=5 ²⁷, N= 10 ³⁸, N = 19 ³⁹, N= 26 ¹ to N=40 ⁴⁰. In the study of Cabrita et. al. random slopes could not be included in the multilevel regression analysis because of the sample size being too small to validly estimate all associated parameters, but an individual analysis with linear regression models with random intercept has been made.³⁸ Other studies using ESM in a population between 19 to 40 patients have shown that clinically relevant differences could be detected using an alpha of 0.05.^{1,39-41} However, epidemiologic literature suggest that as a rule-of-thumb, a sample of at least N = 50 is required to evaluate construct validity^{42,43} and to recognize a factor pattern.⁴⁴ Therefore, we need to include at least 50 participants.

Empirical studies using ESM showed that about 5% to 23.2% of the patients did not comply (defined as completing the ESM questionnaire in less than 50% of the beeps).^{1,27,38-41} Taking into account a conservative non-valid ESM data rate of 23%, a sample size of 66 patients is needed to obtain 50 ESM questionnaires that can be used for the analysis.

4. METHODS

4.1 Study parameters/endpoints

Divided in three parts in accordance with the study objectives.

4.1.1 Part I Comparison of the ESM vs. SR-BDs

Main study parameter/endpoint

- Urgency scores as measured by two self-report measures:
 - The ESM tool (*i.e.* momentary measurement)
 - The sensation-related bladder diary (*i.e.* retrospective measurement with a recall period of several minutes)

Secondary study parameters/endpoints (if applicable)

- Symptom scores (other than urgency) as measured using the ESM tool:
 - Micturition habits, *i.e.* number of micturitions each day and the force of the urinary stream using the Visual Prostate Symptom Score (VPSS)
- Symptom scores (other than urgency) as measured using the single-time retrospective questionnaires:
 - Urological symptoms:
 - Female participants: OABq, ICIQ-FLUTS, 3IQ
 - Male participants: OABq, ICIQ-MLUTS, 3 IQ, IPSS, IIEF-5

4.1.2 Part II Validation

Main study parameter/endpoint

- Urgency scores as measured by two self-report measures:
 - The ESM tool (*i.e.* momentary measurement)
 - The sensation-related bladder diary (*i.e.* retrospective measurement with a recall period of several minutes)

Secondary study parameters/endpoints (if applicable)

- Symptom scores (other than urgency) as measured using the ESM tool:
 - Micturition habits, *i.e.* number of micturitions each day and the force of the urinary stream using the Visual Prostate Symptom Score (VPSS) (see Figure 2).
 - Gastrointestinal symptoms
 - Psychological symptoms
 - Gynaecological symptoms
 - Extra-intestinal somatic symptoms

- Data on context and environment at each time an ESM questionnaire is completed
- Symptom scores (other than urgency) as measured using the sensationrelated bladder diary:
 - Micturition habits, *i.e.* number of micturitions each day
- Symptom scores (other than urgency) as measured using the single-time retrospective questionnaires:
 - Urological symptoms:
 - Female participants: OABq, ICIQ-FLUTS, 3IQ
 - Male participants: OABq, ICIQ-MLUTS, 3 IQ, IPSS, IIEF-5
 - Psychological symptoms: HADS
 - Gynaecological symptoms : Questionnaire Werkgroep Bekkenbodem NVOG
 - Extra-intestinal symptoms and Quality of Life scores: SF-36

Figure 2. The Visual Prostate Symptom Score.

